3 LIST OF ABBREVIATIONS AND DEFINITION OF TERMS

1	 Ferm	Definition

3q4wk Three times every four weeks

ADA Anti-drug antibody

ADC Antibody drug conjugate

AE Adverse event

ALT Alanine aminotransferase
ANC Absolute neutrophil count

aPTT Activated partial thromboplastin time

ASA Acetylsalicylic acid

AST Aspartate aminotransferase

AUC Area-under-the-concentration-time curve

BMI Body mass index BSA Body surface area

cfDNA Cell-free deoxyribonucleic acid
CFR Code of Federal Regulations
C_{max} Maximum concentration

CMV Cytomegalovirus

COPD Chronic obstructive pulmonary disease

CR Complete Response

CRO Clinical research organization

CRPC Castration-resistant prostate cancer

CT Computerized tomography

CTCAE Common Terminology Criteria for Adverse Events

CYP Cytochrome P450
DLT Dose limiting toxicity

DMC Data Monitoring Committee

DNA Deoxyribonucleic acid
DoR Duration of Response
ECG Electrocardiogram

ECOG Eastern Cooperative Oncology Group

eCRF Electronic case report form

EGFR Epidermal growth factor receptor EMA European Medicines Agency

EOT End of Trial

EU European Union

Final 5.0 (incorporating Protocol Amendment 4) 06 Jul 2017

Term Definition

FDA Food and Drug Administration

FIH First-in-human

FVII, FIX, FX Factor VII, factor IX, factor X

FVIIa, FIXa, FXa Activated factor VII/factor IX/factor X

GCP Good Clinical Practice

G-CSF Granulocyte colony stimulating factor

GI Gastrointestinal
HBc Hepatitis B core
HBs Hepatitis B surface

HBsAg Hepatitis B surface antigen

HCV Hepatitis C virus

HNSTD Highest non-severely toxic dose

HPV Human papilloma virus

HuMax Tissue Factor antibody drug conjugate (tisotumab vedotin)

ICF Informed Consent Form

ICH International Council for Harmonisation

IEC Independent Ethics Committee

Ig Immunoglobulin

IHC Immunohistochemistry

IMP Investigational Medicinal Product

IND Investigational New Drug
INR International normalized ratio
IRB Independent Review Board

LD Longest diameter

MedDRA Medical Dictionary for Regulatory Activities

MMAE Monomethyl auristatin E mRNA Messenger ribonucleic acid MTD Maximum tolerated dose

NCCN National Comprehensive Cancer Network

NCI National Cancer Institute

NSAID Nonsteroidal anti-inflammatory drugs

NSCLC Non-small cell lung cancer
ORR Objective response rate
PAR-2 Protease activated receptor 2
PCR Polymerase chain reaction

Final 5.0 (incorporating Protocol Amendment 4) 06 Jul 2017

Term Definition

PD Progressive disease

PFS Progression-Free Survival

P-gp P-glycoprotein
PK Pharmacokinetic(s)
PR Partial Response

PSA Prostate specific antigen

PT Prothrombin time q3wk Every three weeks

qRT-PCR Real-time quantitative polymerase chain reaction
QTcF QT interval as corrected by Fridericia's formula
RECIST Response Evaluation Criteria In Solid Tumors

RP2D Recommended phase II dose

SAE Serious adverse event SAP Statistical analysis plan

SCCHN Squamous cell carcinoma of the head and neck

SD Stable Disease SoC Standard of care

SUSAR Suspected unexpected serious adverse reaction

TEG Thromboelastography

TEN Toxic epidermal necrolysis

TF Tissue factor

TMA Tissue microarray

T_{max} Time of maximum concentration

ULN Upper limit of normal UK United Kingdom

USA United States of America

vc Valine citrulline

VEGF Vascular endothelial growth factor

WHO Drug World Health Organization Drug Reference Dictionary

WMA World Medical Association

Final 5.0 (incorporating Protocol Amendment 4) 06 Jul 2017

4 ETHICS

4.1 Ethics Committee

This trial will be conducted in compliance with independent ethics committee (IEC)/institutional review board (IRB) and International Council for Harmonisation (ICH) Good Clinical Practice (GCP) Guidelines - including Title 21 Part 56 of the United States of America (USA) Code of Federal Regulations (CFR) relating to IRBs and GCP as described in the United States Food and Drug Administration (FDA) CFR (21 CFR § 50, 56, 312), in accordance with applicable regulations regarding clinical safety data management (E2A, E2B(R3)), European Community directives 2001/20, 2001/83, 2003/94 and 2005/28 as enacted into local law, and with ICH guidelines regarding scientific integrity (E4, E8, E9 and E10). In addition, this trial will adhere to all local regulatory requirements, and requirements for data protection.

Before initiating a trial, the investigator/institution must have written and dated approval/favorable opinion from the IEC/IRB for the trial protocol/amendment(s), written Informed Consent Form (ICF), any consent form updates, patient recruitment procedures (e.g., advertisements), and any written information to be provided to patients and a statement from the IEC/IRB that they comply with GCP requirements. The IEC/IRB approval must identify the protocol version as well as the documents reviewed.

4.2 Ethical Conduct of the Trial

This trial will be conducted in accordance with the Note for Guidance on GCP (ICH Harmonized Tripartite Guideline E6 (R1); FDA CFR (21 CFR § 50, 56, 312)), Declaration of Helsinki (Fortaleza 2013, Appendix 3) and all applicable regulatory requirements.

4.3 Patient Information and Consent

The investigator will explain the benefits and risks of participation in the trial to each patient and will obtain written informed consent. Written informed consent must be obtained prior to the patient entering the trial and before initiation of any trial related procedure (including administration of trial drug).

The IEC/IRB-approved information and consent form that is used must be in language readily understood by the patient. Each patient's original consent form personally signed and dated by the patient and by the person who conducted the informed consent discussion, will be retained by the investigator. The investigator will supply all enrolled patients with a copy of their signed informed consent.

The consent form may need to be revised during the trial; should important new information become available that may be relevant to the safety and procedures of the patient. In this instance approval should always be given by the IEC/IRB and existing patients informed of the changes and reconsented. This is documented in the same way as previously described.

The investigator should, with the consent of the patient, inform the patient's primary physician about participation in the clinical trial.

Final 5.0 (incorporating Protocol Amendment 4) 06 Jul 2017

6 INTRODUCTION

Tisotumab vedotin (HuMax®-TF-ADC

Tisotumab vedotin (HuMax®-TF-ADC

Tisotumah vedotin (HuMax®-TF-ADC	Final 5.0 (incorporating Protocol Amendment 4)

Protocol No.GEN702 Tisotumab vedotin (HuMax®-TF-ADC Final 5.0 (incorporating Protocol Amendment 4) 06 Jul 2017 in mixed solid tumors

Tisotumab vedotin (HuMax®-TF-ADC Final 5.0 (incorporating Protocol Amendment 4)

Tisotumab vedotin (HuMax®-TF-ADC	Final 5.0 (incorporating Protocol Amendment 4)

Final 5.0 (incorporating Protocol Amendment 4) 06 Jul 2017

Final 5.0 (incorporating Protocol Amendment 4) 06 Jul 2017

Final 5.0 (incorporating Protocol Amendment 4) 06 Jul 2017

Tisotumab vedotin (HuMax®-TF-ADC in mixed solid tumors

Final 5.0 (incorporating Protocol Amendment 4) in mixed solid tumors

Final 5.0 (incorporating Protocol Amendment 4) in mixed solid tumors

Final 5.0 (incorporating Protocol Amendment 4) 06 Jul 2017

7 TRIAL OBJECTIVES AND ENDPOINTS

7.1 Trial Objectives

7.1.1 Primary Trial Objective

To establish the tolerability of tisotumab vedotin (HuMax-TF-ADC) dosed 3q4wk in a mixed population of patients with specified solid tumors.

7.1.2 Secondary Trial Objectives

- To determine the MTD and the RP2D of tisotumab vedotin (HuMax-TF-ADC) dosed 3q4wk.
- To establish the PK profile of tisotumab vedotin (HuMax-TF-ADC) dosed 3q4wk.
- To evaluate the anti-tumor activity of tisotumab vedotin (HuMax-TF-ADC) dosed 3q4wk in a mixed population of patients with specified solid tumors.

Trial objectives remain unchanged despite the protocol updates related to implementation of the urgent safety measure (Protocol Amendment 4.0).

7.2 Trial Endpoints

7.2.1 Primary Endpoint

The primary endpoint is the evaluation of AEs: incidences of AEs, SAEs, infusion-related AEs, CTCAE grade \geq 3 AEs and AEs related to trial drug during the trial.

7.2.2 Secondary Endpoints

- Safety laboratory parameters (hematology, biochemistry, coagulation factors and flow cytometry)
- Skin disorders
- Bleeding events
- Neuropathy
- PK parameters (clearance, volume of distribution and AUC [AUC0-Clast and AUC0-∞], Cmax, time of Cmax [Tmax], pre-dose values, and half-life of tisotumab vedotin (HuMax-TF-ADC) and free toxin [MMAE])
- Immunogenicity of tisotumab vedotin (HuMax-TF-ADC) (human anti-human antibodies)
- Anti-tumor activity measured by tumor shrinkage (based on CT-scan evaluations), change in PSA and CA 125
- Objective Response (Complete Response [CR] or PR), Disease Control (CR, PR or SD), Progression-Free Survival (PFS) and Duration of Response (DoR)

Final 5.0 (incorporating Protocol Amendment 4) 06 Jul 2017

7.2.3 Research Endpoints

- TF expression in tumor biopsies
- Circulating TF
- cfDNA

Final 5.0 (incorporating Protocol Amendment 4) 06 Jul 2017

8 INVESTIGATIONAL PLAN

8.1 Overall Trial Design and Plan

This is an open-label, multicenter safety trial of tisotumab vedotin (HuMax-TF-ADC) in a mixed population of patients with solid tumors known to express TF and where the use of systemically administered tubulin inhibitors is part of SoC.

The trial consists of two parts; the initial phase I Dose Escalation part is followed by a phase II Cohort Expansion part.

Dose Escalation Part

The phase I Dose Escalation part of the trial is a standard 3 (+3) design which will evaluate tisotumab vedotin (HuMax-TF-ADC) at doses of 0.9 mg/kg and up to a maximum of 1.5 mg/kg (0.9, 1.2, and 1.5 mg/kg).

[figure not shown]
In the absence of unacceptable first cycle toxicities, doses are escalated in the subsequent cohorts, as deemed appropriate by the DMC and confirmed by sponsor. If unacceptable first cycle toxicities are observed, cohorts will be expanded from three to six patients. Depending on the nature of the observed event, the DMC may require that at least one patient of the additional three patients to be enrolled at the same dose level should have the same cancer type as the patient experiencing the event. If a patient withdraws prior to completing the first treatment cycle, the sponsor should replace the patient, unless the withdrawal is due to a DLT. Further details of the dose escalation steps are provided in Section 8.4.7.1.

In each dose cohort, the initial three patients enrolled must include at least two different cancer types. Patients will be treated for four cycles or until the patient withdraws from the treatment/trial due to the withdrawal criteria. Patients showing clinical benefit, defined as SD or better, can receive up to a maximum of eight additional treatment cycles (for a maximum of 12 cycles in total).

At the end of this period, Genmab will ensure provision of continued treatment to patients with clinical benefit defined as SD or better, until unacceptable toxicity or progressive disease (PD) is observed.

See Figure 3 below for illustration.

Figure 3: Dose Levels and Cohorts

CE=Cohort Expansion; DE=Dose Escalation

Twelve cycles are expected to correspond to 48 weeks.

Final 5.0 (incorporating Protocol Amendment 4) 06 Jul 2017

Cohort Expansion Part

Patients in the Cohort Expansion part will be treated with the RP2D from the Dose Escalation part. Patients may receive up to nine cycles of treatment. Reduced dose can be administered in accordance with the mitigation strategies (Section 8.4.4 to 8.4.5.6) or at the discretion of the treating physician based on individual patient observed toxicity profile and quality of life evaluation, and after consultation and agreement by the sponsor Medical Officer.

The specific indications for the Cohort Expansion part will be decided once the RP2D has been determined. Then, inclusion and exclusion criteria for a reduced number of previous lines of treatment will be specified for all potential indications.

[figure not shown]
At the end of the trial, Genmab will ensure provision of continued treatment to patients with clinical benefit defined as SD or better, until unacceptable toxicity or PD is observed. This will be done through a separate extension trial protocol.

Patients will be treated with up to nine cycles. The treatment period will last for up to 36 weeks (or less after changing to the once q3wk dosing scheme) or until unacceptable toxicity or disease progression at the discretion of the treating physician. The treatment duration is shortened compared to the Dose Escalation part in order to align with the treatment duration in the GEN701 trial and since patients with clinical benefit will be ensured continued treatment beyond this duration if so desired.

Severe ocular toxicity has been observed in the dose dense program 1.2 mg/kg 3q4wk and an urgent safety Protocol Amendment 4.0 has been implemented. No patients will further receive the dosing schedule 3q4wk; instead, tisotumab vedotin (HuMax-TF-ADC) 2.0 mg/kg will be administrated once q3wk on Day 1 of each 21-day cycle regardless of the prior dose(s) administered. The next dose of tisotumab vedotin cannot be administered until at least 21 days have elapsed since the last administration.

Figure 4: Dose Scheme for the Cohort Expansion Part After Urgent Safety Measurepresents the new dosing scheme according to the implementation of the urgent safety measure (Protocol Amendment 4.0):

Figure 4: Dose Scheme for the Cohort Expansion Part After Urgent Safety Measure

CE=Cohort Expansion

Nine cycles are expected to correspond to approximately 27 weeks.

Final 5.0 (incorporating Protocol Amendment 4) 06 Jul 2017

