The Dose Escalation part is a standard 3 (+3) design. In each dose cohort, the initial three patients must include at least two different cancer types. A maximum of three dose levels is anticipated. Patients may receive up to 12 cycles of treatment.

The Cohort Expansion part will have a parallel group design, with a minimum of 20 and a maximum of 30 patients in two or three indication arms. Patients in the Cohort Expansion part will be treated with the RP2D from the Dose Escalation part. Patients may receive up to nine cycles of treatment.

A Data Monitoring Committee (DMC) will evaluate safety data during the Dose Escalation part of the trial and will convene in the event of safety signals in the Cohort Expansion part of the trial.

Severe ocular toxicity has been observed at 1.2 mg/kg 3q4wk (the RP2D for the Cohort Expansion part), and an urgent safety Protocol Amendment 4.0 has been implemented. Patients will not further receive the dosing schedule 3q4wk; instead tisotumab vedotin 2.0 mg/kg will be administered once every three weeks (q3wk).

TRIAL POPULATION AND MAIN CRITERIA FOR INCLUSION/EXCLUSION:

The patient population in the Dose Escalation part will encompass patients with advanced (locally advanced and/or metastatic) cancer of the ovary, cervix, endometrium, bladder, prostate (castration-resistant prostate cancer [CRPC]), esophagus or lung (non-small cell lung cancer [NSCLC]) who have failed available standard

Final 5.0 (incorporating Protocol Amendment 4) 06 Jul 2017

treatments or who are not candidates for standard therapy. The specific indications for the Cohort Expansion part will be decided once the RP2D has been determined from the Dose Escalation part.

Patients cannot be enrolled before all inclusion criteria (including test results) are confirmed.

Inclusion Criteria:

- For the Dose Escalation part: Patients with relapsed, advanced and/or metastatic cancer of the ovary, cervix, endometrium, bladder, prostate, esophagus, or NSCLC who have failed available standard treatments or who are not candidates for standard therapy.
- For the Cohort Expansion part: The specific indications for the Cohort Expansion part will be decided once the RP2D has been determined. After implementation of the urgent safety measure (Protocol Amendment 4), no patients will further receive the 3q4wk schedule; instead, tisotumab vedotin (HuMax-TF-ADC) 2.0 mg/kg will be administered once q3wk.

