8.1.1 Trial Overview

A trial overview is described below. The trial flowcharts are shown in Table 1 and Table 2 for the Dose Escalation part and Table 3 and Table 4 for the Cohort Expansion part according to the initially designed treatment scheme. The trial flowchart for the Cohort Expansion part after implementation of the urgent safety measure (Protocol Amendment 4.0) is shown in Table 5 and Table 6. Trial evaluations by visit are detailed in Section 9.

Table 1: Trial Flow Chart-Dose Escalation Part

Treatment Cycle	Screening				Cycle 1	1				Cycl	e 2-4			Cycle	5-12 ¹		Follow - up	EOT ²	Withd- rawal Safety Follow- up ³	Unsche- duled
Visit Number	0	1^{4}	2	3^{4}	4^{4}	5	6	7	1^{4}	2^4	3^4	4	1^{4}	2^4	3^4	4	1-4	-	-	1-X
Day/Week	≤21 days prior to Visit C1-V1	1d	2d	8d	15d	16d	18d	22d	1d	8d	15d	22d	1d	8d	15d	22d	6 weekly	-	30 days after last dosing	-
Visit window ⁵		-	-	±1d	±1d	+1d	±1d	±1d	±3d	±1d	±1d	±1d	±3d	±1d	±1d	±1 d	±7d	-	±14d	-
Informed Consent	X^6																			
Eligibility Criteria	X																			
Demographics	X																			
Medical History ⁷	X																			
Height and Body Weight ⁸	X	X							X				X					X		
Physical Examination	X	X																X		
Vital Signs ⁹	X	X	X	X	X	X	X	X	X	X	X	X	X	X	X	X		X		X^{10}
ECG ¹¹	X	X							X				X					X		X^{10}
CT-Scan	X^{12}								X^{13}				X^{13}				X	X^{13}		X^{10}
ECOG Performance Status	X	X							X				X					X		X^{10}
Adverse Events	X	X	X	X	X	X	X	X	X	X	X	X	X	X	X	X	X	X	X	X^{10}
Concomitant Medication	X	X	X	X	X	X	X	X	X	X	X	X	X	X	X	X	X	X		X^{10}
Trial Drug Administration		X		X	X				X	X	X		X	X	X					
Bleeding Assessment	X	X	X	X	X	X	X	X	X	X	X		X	X	X			X		

Treatment Cycle	Screening				Cycle 1	1				-	e 2-4			Cycle	5-121		Follow - up	EOT ²	Withd- rawal Safety Follow- up ³	Unsche- duled
Visit Number	0	1^4	2	3^{4}	44	5	6	7	1^4	2^4	3^4	4	1^{4}	2^4	3^4	4	1-4	-	-	1-X
Day/Week	≤ 21 days prior to Visit C1-V1	1d	2d	8d	15d	16d	18d	22d	1d	8d	15d	22d	1d	8d	15d	22d	6 weekly	-	30 days after last dosing	-
Visit window ⁵		-	-	±1d	±1d	+1d	±1d	±1d	±3d	±1d	±1d	±1d	±3d	±1d	±1d	±1 d	±7d	-	±14d	-
Skin Assessment	X	X	X	X	X	X	X	X	X	X	X		X	X	X		X	X		X^{10}
Neuropathy Assessment	X	X		X	X			X	X	X	X	X	X	X	X	X	X	X		X^{10}
Ophthalmological Evaluation	X							X ²²				X^{22}				X^{22}		X^{22}		$X^{10,22}$
Radionuclide Bone Scan ¹⁴	X												X							X^{10}
LABORATORY AS	SSESSMENT	Γ S 15																		
Hematology	X	X	X	X	X	X	X	X	X	X	X	X	X	X	X	X	X	X		X^{10}
Biochemistry	X	X	X	X	X	X	X	X	X	X	Χ	X	X	X	X	X	X	X		X^{10}

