8.4.1 Treatments Administered

The investigator must ensure that the trial drug will be used only in accordance with the protocol.

Tisotumab vedotin (HuMax-TF-ADC) will be administered as an intravenous infusion on Days 1, 8 and 15 of each cycle (one treatment cycle is 28 days).

After implementation of the urgent safety measure (Protocol Amendment 4), tisotumab vedotin (HuMax-TF-ADC) 2.0 mg/kg will be administrated once q3wk on Day 1 (one treatment cycle is 21 days), regardless of the prior dose(s) administered. The next dose of tisotumab vedotin (HuMax-TF-ADC) cannot be administered until at least 21 days have elapsed since the last administration.

Each patient's dose will be calculated based on the patient's weight rounded to the nearest kilogram, i.e., assigned cohort dose in mg/kg × body weight in kg. The weight used per cycle should be the weight taken in connection with the first dosing visit of the current cycle (see Section 10.3). For patients whose body mass index (BMI) is greater than 30 kg/m², the investigator should use a weight that, based on the patient's height, corresponds to a maximum BMI of 30.

The dose is calculated according to the following formula if BMI is greater than 30kg/m²:

Dose
$$(mg) = x (mg/kg) * 30 (kg/m2) * height (m) * height (m)$$

Final 5.0 (incorporating Protocol Amendment 4) 06 Jul 2017

Tisotumab vedotin (HuMax-TF-ADC) will be administered over a minimum of 30 minutes. If infusion-related events emerge, refer to Section 8.4.4. The infusion is complete when the infusion line has been flushed with a minimum 15 mL saline. Preventive eye therapy should be administered in relation to infusions as detailed in Section 8.4.5.3.

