9.1.2 Dose Escalation Part: Treatment

The Dose Escalation part of the trial must be run in phase I units with cardiopulmonary resuscitation rescue equipment available and fast access to emergency units.

Tisotumab vedotin (HuMax-TF-ADC) will be administered 3q4wk, on Day 1, Day 8 and Day 15 of each 28-day treatment cycle. Dose escalation to MTD is anticipated to involve approximately three dose levels with an anticipated maximal exposure of 1.5 mg/kg.

Throughout the infusion patients will be under surveillance by trial personnel. The physician supervising the trial drug infusion must be readily accessible for assistance during the day of infusion.

Final 5.0 (incorporating Protocol Amendment 4)
06 Jul 2017

The investigator must have evaluated the patient's eligibility and must confirm receipt of sponsor decision and patient number before the patient's first infusion. This form will have to be validated by the sponsor and/or designee and will serve to assign the patient number.

The patients will receive four cycles of tisotumab vedotin (HuMax-TF-ADC) at four-week intervals. Thus, the treatment period will last for 16 weeks, or until the patient withdraws from the treatment/trial due to withdrawal criteria.

During infusions the patient should be closely monitored including vital signs and general assessment for at least two hours following administration of tisotumab vedotin (HuMax-TF-ADC) in a setting with resuscitation equipment and other agents necessary to treat anaphylaxis (e.g., epinephrine, corticosteroids, intravenous antihistamines, bronchodilators and oxygen). Patients requiring treatment for infusion-related reactions should be monitored until the resolution of the event.

9.1.2.1 Dose Escalation Part: Cycle 1

During Cycle 1, seven trial visits will be performed on Days 1, 2, 8, 15, 16, 18 and 22.

9.1.2.2 Dose Escalation Part: Cycles 2 to 4

During Cycles 2 to 4, four trial visits will be performed on Days 1, 8, 15 and 22 of each cycle.

After four cycles, if there is evidence of the patient benefitting from treatment, there is an option to continue in the trial for up to a maximum of eight additional cycles (32 weeks) or until patient withdraws from treatment/the trial due to withdrawal criteria, at the discretion of the treating physician based on the patient status.

9.1.2.3 Dose Escalation Part: Cycles 5 to 12

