12.3 Statistical Methods

The presentations will be done separately for the Dose Escalation part and the Cohort Expansion part.

In the reporting of the Dose Escalation part tables will report by cohort, while in the Cohort Expansion part tables will report by indication.

The shift from the 3q4wk dosing to the once q3wk dosing in the Cohort Expansion part may lead to a need for reporting some tables by dosing schedule. This will be described as appropriate in the SAP.

No formal statistical tests will be performed.

For efficacy analyses, the quartile estimates of PFS and DoR from the Kaplan-Meier product limit algorithm will be presented (Kaplan and Meier, 1958). The 2-sided 95% confidence interval will be presented as well. The number of events may be small, and thereby limit use of the Kaplan-Meier method to provide reliable information. In this case, descriptive statistics (e.g., n, mean, standard deviation, median, minimum and maximum) for PFS or DoR will be presented. Objective response (CR or PR) rate will be determined along with the corresponding 2-sided 95% exact binomial confidence interval.

All data will be listed. Baseline is defined as the latest available measurement made before the first treatment with tisotumab vedotin (HuMax-TF-ADC).

A patient will be considered as having completed the trial when all planned trial visits have been performed.

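### The protocol does not settle whether the Amendment 4 stop of 3q4wk dosing applies to the Dose Escalation part: unscoped text moves patients to q3wk, while the Dose Escalation text and Table 1 still order 3q4wk up to Cycle 12

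*Protocol*

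**What the plan says.** **Text that ends or replaces 3q4wk without naming a part**

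- Synopsis, trial design: "Patients will not further receive the dosing schedule 3q4wk; instead tisotumab vedotin 2.0 mg/kg will be administered once every three weeks (q3wk"). The treatment paragraph of the Synopsis says the same in similar words.
- Section 8.4.1, common to both parts: after Amendment 4 the 2.0 mg/kg dose "will be administrated once q3wk on Day 1 (one treatment cycle is 21 days), regardless of the prior dose(s) administered".
- Section 8.4.5 introduces the dose-modification plans as written for the q3wk scheme.

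**Text that places the stop in the Cohort Expansion part**

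- Section 8.1, under the Cohort Expansion sub-heading: "No patients will further receive the dosing schedule 3q4wk". Figure 4, titled for that part, follows.
- The Cohort Expansion paragraphs of Section 8.1.1.2 and of inclusion criterion 1.

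**Text that keeps 3q4wk for the Dose Escalation part**

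- Section 9.1.2: the drug "will be administered 3q4wk, on Day 1, Day 8 and Day 15 of each 28-day treatment cycle". Section 8.1.1.2 agrees, and Section 9.1.2.3 keeps weekly visits through Cycles 5 to 12.
- Section 8.1, on the length of treatment: "Twelve cycles are expected to correspond to 48 weeks".
- "Table 1: Trial Flow Chart-Dose Escalation Part" marks drug on Days 1, 8 and 15 in every cycle block to Cycle 12.

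The titles of Tables 3 and 4 (Cohort Expansion) carry the word SUPERSEDED; those of Tables 1 and 2 do not. Tables 5 and 6, which apply after the urgent safety measure, are for Cohort Expansion only.

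**The concern.** Amendment 4 is an urgent safety measure made because severe ocular toxicity was seen at 1.2 mg/kg 3q4wk. The reach of such a measure should not need interpretation. A site with a Dose Escalation patient still on treatment would find Synopsis and Section 8.4.1 text that moves the patient to q3wk. It would also find part-specific text and a flow chart that continue 3q4wk.

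Neither reading can be carried out cleanly. If the patient switches, no flow chart covers a Dose Escalation patient on 21-day cycles. If the patient does not switch, the common dose-modification and assessment sections no longer fit that patient's schedule. At stake are dosing, ocular dose reduction and the timing of scans and examinations.

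**Working it through.** **1. Durations in the plan.** Weeks = cycles × cycle length in days / 7.

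- Dose Escalation: 12 × 28 / 7 = 48 weeks, as Section 8.1 states, with up to 12 × 3 = 36 infusions.
- Cohort Expansion before Amendment 4: 9 × 28 / 7 = 36 weeks, as stated.
- Cohort Expansion after Amendment 4: 9 × 21 / 7 = 27 weeks, as stated.

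The durations are internally correct. The 48 weeks belongs to 28-day cycles, so the Dose Escalation text was left on the 3q4wk scheme.

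**2. Passages side by side.**

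| Item | Text that names no part | Dose Escalation text or Table 1 |
|---|---|---|
| Dosing | Synopsis, 8.4.1: 2.0 mg/kg on Day 1 of 21 days | 8.1.1.2, 9.1.2, Table 1: Days 1, 8 and 15 of 28 days, to Cycle 12 |
| CT | 10.7: every six weeks, after every second cycle (2 × 21 / 7 = 6) | Table 1 note 13: Day 1 of Cycles 3, 5, 7, 9 and 11 (2 × 28 / 7 = 8 weeks) |
| Bone scan (CRPC) | 10.15: every 12 weeks, Cycles 5 and 9 (4 × 21 / 7 = 12) | Table 1 note 14: every 16 weeks, same cycles (4 × 28 / 7 = 16) |
| Skin | 8.4.5.1: Days 1 and 15 of Cycle 1, then Day 1 | Table 1: every Cycle 1 visit, then Days 1, 8 and 15 |
| Ocular dose steps | 8.4.5.3: from 2.0, 1.3 or 0.9 mg/kg, the last described as every third week | 8.1: planned levels 0.9, 1.2 and 1.5 mg/kg, given 3q4wk |

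The common sections therefore fit q3wk only. One caution on the bone scan: note 14 of Table 5 also says 16 weeks, although Cycles 5 and 9 lie 12 weeks apart on 21-day cycles. That mismatch shows incomplete updating and does not by itself show what scope was intended.

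**3. Planned dose per 28 days.** For 3q4wk, 3 × level; for q3wk, 2.0 × 28 / 21 = 2.67 mg/kg.

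| Level, 3q4wk | Per 28 days | Ratio to 2.67 |
|---|---|---|
| 0.9 mg/kg | 3 × 0.9 = 2.7 mg/kg | 1.01 |
| 1.2 mg/kg | 3 × 1.2 = 3.6 mg/kg | 1.35 |
| 1.5 mg/kg | 3 × 1.5 = 4.5 mg/kg | 1.69 |

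These figures compare scheduled dose only.

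**4. Is the scope settled anywhere?** No sentence in the text at hand says that Dose Escalation dosing has ended, that these patients are exempt, or that they switch.

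**The case against.** The best case for the plan is that the measure concerns Cohort Expansion only. The sentence in Section 8.1 stands under that heading, and Section 8.1.1.2 and inclusion criterion 1 place the stop there too. In the Synopsis, the stop is tied to 1.2 mg/kg as the dose chosen for the expansion. The openings of Sections 9 and 10 group Table 1 with Table 3 as the initially designed scheme, so a reader has some notice of Table 1's status even without the word SUPERSEDED. And if no Dose Escalation patient is on drug, nothing conflicts in practice.

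Much of this stands, and it rules out several stronger readings:

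- A reader might infer that the Section 8.1 sentence alone contradicts Table 1. Given its heading, it does not. The conflict rests on the Synopsis and Section 8.4.1.
- A reader might infer that patients are still receiving the stopped schedule. The documents do not show this. The expansion dose was already chosen by this version, and the Introduction is missing from the public copy, so silence proves nothing either way. The 48-week maximum shows only that overlap cannot be excluded; it does not measure it.
- A reader might infer that events after a switch have no place in the analysis, because Section 12.3 says "The shift from the 3q4wk dosing to the once q3wk dosing in the Cohort Expansion part may lead to a need for reporting some tables" and mentions no other part. Section 12.1, however, leaves the analysis of all patients treated after Amendment 4 to an SAP update, with no limit to a part. This is not a defect of the protocol.
- A reader might take the dose ratios as a measure of risk. They are not, and at 0.9 mg/kg the planned doses are nearly equal.
- The ocular dose table is not wrong for patients who switch, since they go to 2.0 mg/kg whatever they had before. It lacks a starting row only for a patient kept at 1.2 or 1.5 mg/kg.

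What the objection does not remove is that the Synopsis and Section 8.4.1 name no part. If the measure is for Cohort Expansion only, Sections 8.4.5, 10.7 and 10.15 then give q3wk rules to patients on 28-day cycles.

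**Conclusion.** The point holds as a contradiction about scope in the protocol's operative text. Dosing, dose modification, CT, bone-scan and skin-assessment instructions all differ according to whether a Dose Escalation patient is read as covered by Amendment 4. The consequence for patients is conditional: it arises only if at least one Dose Escalation patient was still on treatment when the amendment took effect, which the documents neither state nor exclude. For such a patient the two readings differ in planned dose by a factor of 1.01, 1.35 or 1.69, according to the assigned level. No test, sample size or analysis rule is affected. Because the measure addresses severe ocular toxicity and clarification costs little, the text should be corrected.

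**What to change.** Reconcile the passages with one explicit statement: which part or parts Amendment 4 covers, or that no Dose Escalation patient remains on treatment.

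- **If Dose Escalation is covered:** mark the remaining-cycle columns of Tables 1 and 2 as superseded, name the flow chart that applies to these patients, and align Sections 8.1, 8.1.1.2, 9.1.2 and 9.1.2.3.
- **If it is not covered:** limit the wording in the Synopsis and in Sections 8.1 and 8.4.1 to the Cohort Expansion part, and state which dose-modification, CT, bone-scan and skin-assessment timing applies to Dose Escalation patients (Sections 8.4.5, 10.7 and 10.15).

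Which schedule applies is a clinical decision for the sponsor, and this review takes no position on it. The cost of the clarification is wording in the Synopsis, the sections named and the table titles. The clarification itself needs no extra patients or procedures.
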